### **CLINICAL STUDY REPORT AND PUBLICATIONS**

A signatory investigator must be selected to sign the clinical study report.

For this protocol, the signatory investigator will be selected as appropriate based on one or more of the following criteria:

- External principal investigator designated at protocol development
- National Coordinating investigator
- Study Steering Committee chair or their designee
- Participant recruitment (eg, among the top quartile of enrollers)
- Involvement in trial design
- Regional representation (eg, among top quartile of enrollers from a specified region or country)
- Other criteria (as determined by the study team)

The data collected during this study are confidential and proprietary to Sponsor or designee. Any publications or abstracts arising from this study must adhere to the publication requirements set forth in the clinical trial agreement (CTA) governing study site or investigator participation in the study. These requirements include, but are not limited to, submitting proposed publications to Sponsor or designee at the earliest practicable time prior to submission or presentation and otherwise within the time period set forth in the CTA.

### APPENDIX 3      **ADVERSE EVENTS AND SERIOUS ADVERSE EVENTS: DEFINITIONS AND PROCEDURES FOR RECORDING, EVALUATING, FOLLOW-UP, AND REPORTING**

#### Adverse Events

Adverse Event Definition:
An adverse event (AE) is defined as any new untoward medical occurrence or worsening of a preexisting medical condition in a clinical investigation participant administered study drug and that does not necessarily have a causal relationship with this treatment.
An AE can therefore be any unfavorable and unintended sign (such as an abnormal laboratory finding), symptom, or disease temporally associated with the use of study drug, whether or not considered related to the study drug.
Events Meeting the AE Definition

• Any abnormal laboratory test results (hematology, clinical chemistry, or urinalysis) or results from other safety assessments (eg, ECG, radiological scans, vital signs measurements), including those that worsen from baseline, considered clinically significant in the medical and scientific judgment of the investigator. Note that abnormal lab tests or other safety assessments should only be reported as AEs if the final diagnosis is not available. Once the final diagnosis is known, the reported term should be updated to be the diagnosis.

• Exacerbation of a chronic or intermittent pre-existing condition including either an increase in frequency and/or intensity of the condition.

• New conditions detected or diagnosed after study intervention administration even though it may have been present before the start of the study.

• Signs, symptoms, or the clinical sequelae of a suspected drug-drug interaction.

• Signs, symptoms, or the clinical sequelae of a suspected overdose of either study intervention or a concomitant medication. Overdose, as a verbatim term (as reported by the investigator), should not be reported as an AE/SAE unless it is an intentional overdose taken with possible suicidal/self-harming intent. Such overdoses should be reported regardless of sequelae and should specify "intentional overdose" as the verbatim term.

Events NOT Meeting the AE Definition


• Medical or surgical procedure (eg, endoscopy, appendectomy): the condition that leads to the procedure is the AE.

• Situations in which an untoward medical occurrence did not occur (social and/or convenience admission to a hospital).

## Definition of SAE

If an event is not an AE per definition above, then it cannot be an SAE even if serious conditions are met.

## Serious Adverse Events

Serious Adverse Event (SAE) is defined as any untoward medical occurrence that, at any dose:
Results in death
Is life-threatening (defined as an event in which the participant was at risk of death at the time of the event; it does not refer to an event which hypothetically might have caused death if it were more severe)
Requires inpatient hospitalization or causes prolongation of existing hospitalization (see note below) Note: The following hospitalizations are not considered SAEs in BMS clinical studies: 
 
• a visit to the emergency room or other hospital department < 24 hours, that does not result in admission (unless considered an important medical or life-threatening event)
 
• elective surgery, planned prior to signing consent
 
• admissions as per protocol for a planned medical/surgical procedure
 
• routine health assessment requiring admission for baseline/trending of health status (eg, routine colonoscopy)
 
• medical/surgical admission other than to remedy ill health and planned prior to entry into the study. Appropriate documentation is required in these cases.
 
• admission encountered for another life circumstance that carries no bearing on health status and requires no medical/surgical intervention (eg, lack of housing, economic inadequacy, caregiver respite, family circumstances, administrative reason)
 
• admission for administration of anticancer therapy in the absence of any other SAEs (applies to oncology protocols)
 

Results in persistent or significant disability/incapacity
Is a congenital anomaly/birth defect
Is an important medical event (defined as a medical event(s) that may not be immediately life-threatening or result in death or hospitalization but, based upon appropriate medical and scientific judgment, may jeopardize the participant or may require intervention [e.g., medical, surgical] to prevent one of the other serious outcomes listed in the definition above.) Examples of such events include, but are not limited to, intensive treatment in an emergency room or at home for allergic bronchospasm; blood dyscrasias or convulsions that do not result in hospitalization.) Potential drug-induced liver injury (DILI) is also considered an important medical event. (See Section 8.5.8 for the definition of potential DILI.)

Pregnancy and potential drug-induced liver injury (DILI) must follow the same transmission timing and processes to BMS as used for SAEs (see [Section 8.5.6](#) for reporting pregnancies).

### Evaluating AEs and SAEs

Assessment of Intensity

The intensity of AEs is determined by a physician and will use the following levels:
 

• Mild: An event that is easily tolerated by the subject, causing minimal discomfort, and not interfering with everyday activities.

• Moderate: An event that causes sufficient discomfort and interferes with normal everyday activities.

• Severe: An event that prevents normal everyday activities. An AE that is assessed as severe should not be confused with an SAE. Severe is a category utilized for rating the intensity of an event; and both AEs and SAEs can be assessed as severe.

Assessment of Causality

• The investigator is obligated to assess the relationship between study intervention and each occurrence of each AE/SAE. A “reasonable possibility of a relationship” conveys that there are facts, evidences, and/or arguments to suggest a causal relationship rather than a relationship cannot be ruled out.

• The investigator will use clinical judgment to determine the relationship.

• Alternative causes, such as underlying disease(s), concomitant therapy, and other risk factors, as well as the temporal relationship of the event to study intervention administration will be considered and investigated.

• The investigator will also consult the Investigator’s Brochure (IB) and/or Product Information, for marketed products, in his/her assessment.

• For each AE/SAE, the investigator must document in the medical notes that he/she has reviewed the AE/SAE and has provided an assessment of causality.

• There may be situations in which an SAE has occurred and the investigator has minimal information to include in the initial report to Sponsor. However, it is very important that the investigator always make an assessment of causality for every event before the initial transmission of the SAE data to Sponsor.

• The investigator may change his/her opinion of causality in light of follow-up information and send a SAE follow-up report with the updated causality assessment.

• The causality assessment is one of the criteria used when determining regulatory reporting requirements.

### Follow-up of AEs and SAEs

If only limited information is initially available, follow-up reports are required. (Note: Follow-up SAE reports must include the same investigator term(s) initially reported.)

If an ongoing SAE changes in its intensity or relationship to study treatment or if new information becomes available, the SAE report must be updated and submitted within 24 hours to BMS (or designee) using the same procedure used for transmitting the initial SAE report.

All SAEs must be followed to resolution or stabilization.

### Reporting of SAEs to Sponsor or Designee

SAEs, whether related or not related to study drug, and pregnancies must be reported to [REDACTED] Drug Safety within 24 hours of awareness of the event.

SAEs must be recorded on the SAE Report Form. For studies capturing SAEs through electronic data capture (EDC), electronic submission is the required method for reporting. In the event the electronic system is unavailable for transmission, paper forms must be used and submitted immediately. When paper forms are used, the original paper forms are to remain on site.

Pregnancies must be recorded on a paper Pregnancy Surveillance Form and transmitted via email or confirmed facsimile (fax) transmission to:

**SAE Email Address:** [REDACTED]

## **APPENDIX 4      WOMEN OF CHILDBEARING POTENTIAL DEFINITIONS AND METHODS OF CONTRACEPTION**

### **DEFINITIONS**

#### **Woman of Childbearing Potential (WOCBP)**

A woman is considered fertile following menarche and until becoming postmenopausal unless permanently sterile. Permanent sterilization methods include hysterectomy, bilateral salpingectomy, and bilateral oophorectomy.

#### **Women in the following categories are not considered WOCBP**

- Premenarchal
- Premenopausal female with 1 of the following:
  - Documented hysterectomy
  - Documented bilateral salpingectomy
  - Documented bilateral oophorectomy

Note: Documentation can come from the site personnel's review of the participant's medical records, medical examination, or medical history interview.

- Postmenopausal female
  - A postmenopausal state is defined as 12 months of amenorrhea in a woman over age 45 years in the absence of other biological or physiological causes. In addition, females under the age of 55 years must have a serum follicle-stimulating hormone, (FSH) level > 40 mIU/mL to confirm menopause.

Note: Females treated with hormone replacement therapy, (HRT) are likely to have artificially suppressed FSH levels and may require a washout period in order to obtain a physiologic FSH level. The duration of the washout period is a function of the type of HRT used. The duration of the washout period below are suggested guidelines and the investigators should use their judgement in checking serum FSH levels.

- 1 week minimum for vaginal hormonal products (rings, creams, gels)
- 4 week minimum for transdermal products
- 8 week minimum for oral products

Other parenteral products may require washout periods as long as 6 months. If the serum FSH level is > 40 mIU/mL at any time during the washout period, the woman can be considered postmenopausal.

### **CONTRACEPTION GUIDANCE FOR FEMALE PARTICIPANTS OF CHILDBEARING POTENTIAL**

The contraception requirements for BMS-986165 include the use of at least one highly effective method of contraception during the study and for 33 days after the last dose (5 half-lives [3 days] plus 30 days [duration of ovulatory cycle]). However, the contraception requirements for

mycophenolate mofetil (MMF) exceed those for BMS-986165, so the MMF requirements will apply to this study.

Per the MMF prescribing information, WOCBP must use effective contraception during treatment and for at least 6 weeks after the final dose of this drug. Subjects must be counseled that MMF may reduce the effectiveness of oral contraceptives, and use of additional barrier methods is required.

For this study, WOCBP must choose either one method from Option 1, or two methods from Option 2 as shown below:

Acceptable Contraception for WOCBP in Study IM011073			
Option 1:			
Choose 1	
 
• IUD
 
• Tubal sterilization
 
• Patient’s partner vasectomy
 
		
Option 2:		Hormone Methods (Choose 1)	Barrier Methods (Choose 1)
Choose 1 hormone method AND 1 barrier method	
Estrogen and Progesterone
 
 
• Oral contraceptive
 
• Transdermal patch
 
• Vaginal ring
 
 
Progesterone only
 
 
• Injection
 
• Implant
 
	AND	
 
• Diaphragm with spermicide
 
• Cervical cap with spermicide
 
• Contraceptive sponge
 
• Male condom
 
• Female condom
 

IUD = intrauterine device; WOCBP = women of childbearing potential

Note: Although the MMF prescribing information offers a third option (2 barrier methods), this choice is not sufficient for BMS-986165 and is not acceptable for WOCBP in this study.

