**Table 3: Procedures and Assessments in Part B of IM011073 (52-Week Blinded Treatment Period)**

Visit Number	B1	B2	B3	B4	B5	B6	B7	B8	B9	B10	B11	B12	B13	B14/ EOT a	B15 a	Notes
Study Week/Day	D1	W4 D29 ±3d	W8 D57 ±3d	W12 D85 ±3d	W16 D113 ±3d	W20 D141 ±3d	W24 D169 ±3d	W28 D197 ±3d	W32 D225 ±3d	W36 D253 ±3d	W40 D281 ±3d	W44 D309 ±3d	W48 D337 ±3d	W52 D365 ±3d	28-D FU ±3d	The final study visit (for noncontinuing subjects) will occur 28d±3d after the visit at W52
Confirm study eligibility criteria are still met	X															
Evaluate for randomization	X															
Body weight & vital signs	X	X	X	X	X	X	X	X	X	X	X	X	X	X	X	BP and HR should be measured after the subject has been sitting quietly for at least 5 minutes
Complete physical examination	X	X	X	X	X	X	X	X	X	X	X	X	X	X	X	
Concomitant medications	X	X	X	X	X	X	X	X	X	X	X	X	X	X	X	
12-lead ECG	X	X	X				X						X	X		
AEs and SAEs	X	X	X	X	X	X	X	X	X	X	X	X	X	X	X	Section 8.5
Subject Status Evaluation							X									Section 7.2
Indices of disease activity and damageb																
rSFI		X	X	X	X	X	X	X	X	X	X	X	X	X	X	All systems except renal; clinical component only (not treatment) APPENDIX 17
OSS Flare Index		X	X	X	X	X	X	X	X	X	X	X	X	X	X	APPENDIX 16

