#### **4.1.2.1 Criteria to Continue in Part B With or Without Randomization**

1. Trough MPA concentration  $\geq 1$   $\mu\text{g/mL}$  (this sample will be collected at Visit A3 to allow sufficient time for analysis and reporting of result; for subjects with  $\geq 12$  weeks of MMF at the time of screening, the screening value will be used)
2. The corticosteroid dose (if any) at Visit B1 must not exceed 25 mg/day of prednisone (or equivalent dose of other corticosteroid; see [APPENDIX 6](#))
3. The subject continues to meet all study eligibility criteria (see [Section 5](#)), including the blood pressure requirement (see Exclusion Criterion 2b in [Section 5.2](#))
4. The subject is taking and tolerating target-dose MMF (1.5 to 3.0 g/day) and likely to continue to tolerate the target dose through Week 52

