### 4) Age and Reproductive Status

- a. Men and women aged 18 (or local age of majority) to 75 years inclusive at the time of screening
- b. Women of childbearing potential (WOCBP) must have a negative serum or urine pregnancy test (minimum sensitivity 25 IU/L or equivalent units of beta-human chorionic gonadotropin) at screening, within 24 hours before the first dose of MMF in Part A, and before the first dose of blinded study treatment in Part B.
- c. Women must not be breastfeeding
- d. The contraception requirements for MMF are stricter than those for BMS-986165; therefore the requirements for MMF (see [APPENDIX 4](#)) must be followed throughout study participation and for a period of time after the final dose of MMF or blinded study treatment as follows:
  - i. WOCBP:
    - a. Per the MMF prescribing information, subjects taking MMF must use acceptable contraception (see options in [APPENDIX 4](#)) throughout the study and continue for at least 6 weeks after the final dose of MMF
    - b. Subjects must be counseled that MMF may reduce the effectiveness of oral contraceptives, and use of additional barrier contraceptive methods is required
  - ii. Men who are sexually active with WOCBP:
    - a. Subjects must inform any and all partners of their participation in the study and the need to use contraception during the man's study participation and for at least 90 days after his last dose of MMF
    - b. Per the MMF prescribing information, male subjects taking MMF must continue to use effective contraception and should not donate sperm for at least 90 days after the final dose of MMF

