### 6.1 Mycophenolate Mofetil Target Dose and Dose Modification

For subjects who will be starting MMF in Part A, treatment will be initiated at 500 mg BID. If tolerated, the dose will be increased to a suggested target dose of 1.5 to 2.0 g/day (subjects self-described as Asian) or 2.0 g/day (all others) one week after initiating MMF. Subjects who have been on MMF at a dose of  $\leq 750$  mg/day at the time of screening will follow the same escalation schedule as those starting MMF. For subjects self-described as Black, African American, or of African descent, the dose will be further increased to 3.0 g/day two weeks after initiating MMF. The following suggested target doses of MMF should be reached by the time of randomization:

- 1.5 to 2.0 g/day for subjects self-described as Asian or of Asian descent
- 3.0 g/day for subjects self-described as Black, African American, or of African descent
- 2.0 g/day for all others, with the following exception:

Subjects entering the study on a stable dose of MMF greater than the target may continue that dose if it is no greater than 3.0 g/day. In some non-African subjects, the investigator may believe that it is in the best interest of the subject to use doses higher than 2.0 g/day; this is allowed provided the dose is not higher than the maximum of 3.0 g/day.

From Week 6 of MMF treatment in Part A through the end of Part B, the MMF dose should remain stable with the following exceptions:

- A change from a BID to a three times daily (TID) regimen is permitted as long as the total daily dose remains unchanged
- Per the MMF prescribing information, if neutropenia develops ( $ANC < 1300/\mu L$ ), MMF dosing should be interrupted or the dose reduced, appropriate diagnostic tests should be performed, and the subject should be managed appropriately.

After a subject reaches the target dose, the dose should remain stable through the end of Part B; however, if necessary because of intolerance, the rate of dose increase may be slowed, or the dose may be divided and administered TID, at the discretion of the investigator.

If a subject cannot tolerate the MMF dose or the investigator has concerns about over-immunosuppression, the target dose may be reduced; however, subjects unable to tolerate a minimum dose of 1.5 g/day in Part A should be discontinued from study treatment and will be considered enrollment failures.

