### **CONTRACEPTION GUIDANCE FOR MALE PARTICIPANTS WITH PARTNER(S) OF CHILDBEARING POTENTIAL.**

Male participants with female partners of childbearing potential are eligible to participate if they agree to the following during the treatment and until the end of relevant systemic exposure.

- Inform any and all partner(s) of their participation in a clinical drug study and the need to comply with contraception instructions as directed by the investigator.
- Male participants are required to use a condom for study duration and until the end of relevant systemic exposure defined as 90 days after the end of treatment in the male participant.
- Female partners of males participating in the study to consider use of effective methods of contraception until the end of relevant systemic exposure, defined as 90 days after the end of treatment in the male participant.
- Male participants with a pregnant or breastfeeding partner must agree to remain abstinent from penile vaginal intercourse or use a male condom during each episode of penile penetration during the treatment and until 90 days after the end of treatment.
- Refrain from donating sperm for the duration of the study treatment and for 90 days after the end of treatment.

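### Women's post-treatment contraception has a stated length only from the final MMF dose, so cover can end a few days short of the protocol's own 33 days if MMF stops 10 or more days before BMS-986165

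*Combined protocol and SAP*

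**What the plan says.** Appendix 4 (guidance for female participants) gives BMS-986165 its own period: at least one highly effective method during the study and "for 33 days after the last dose (5 half-lives [3 days] plus 30 days [duration of ovulatory cycle". It then states that the MMF requirements "exceed those for BMS-986165, so the MMF requirements will apply to this study". The MMF period is at least 6 weeks from the last dose of MMF.

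Section 5.1, criterion 4d, makes the MMF requirements govern during study participation and "for a period of time after the final dose of MMF or blinded study treatment as follows". The item for women that follows, 4d(i), gives one length: "throughout the study and continue for at least 6 weeks after the final dose of MMF". No period of stated length for women starts at the last dose of blinded treatment.

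For men, Appendix 4 uses wording that is not tied to one drug: "defined as 90 days after the end of treatment in the male participant". (Criterion 4d(ii) counts from the MMF dose for men as well; nothing is claimed here about men.)

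Table 3 places the end-of-study visit as follows: "The final study visit (for noncontinuing subjects) will occur 28d±3d after the visit at W52".

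**The concern.** The MMF rule replaces the BMS-986165 rule on the premise that it is the stricter one. On duration, that holds only while the two drugs end close together. If MMF ends well before BMS-986165, 6 weeks from MMF can expire before 33 days from BMS-986165. The remaining cover is then only the general duty to use contraception while in the study.

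Appendix 4 did check the permitted methods against both drugs: it rejects the MMF label's option of two barrier methods as insufficient for BMS-986165. Duration did not get the same check.

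What is at stake is a small part of a reproductive-safety margin that the protocol set for itself. The last scheduled pregnancy test (Visit B15) comes before the uncovered days. The pregnancy-notification rule in Section 8.5.6 covers pregnancies on treatment or within 3 days of stopping it. No efficacy or other statistical result is affected.

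**Working it through.** **Inputs**
- BMS-986165 period: 33 days (Appendix 4). It reproduces as 3 + 30 = 33.
- MMF period: at least 6 weeks = 42 days from the final MMF dose (Appendix 4; criterion 4d(i)).
- End-of-study visit: day 28, window 25 to 31 (Table 3).
- Safety follow-up: 30 days after the final dose (Sections 7.1, 7.3 and 8.5.2). Section 7.4 also sets 30 days for outcome data after early discontinuation.

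**Formula.** Let g be the number of days by which the final MMF dose precedes the final BMS-986165 dose. Let V be the day participation ends, counted from the final BMS-986165 dose. Required cover ends on day max(42 − g, V), so

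shortfall = max(0, 33 − max(42 − g, V)).

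The MMF period alone suffices while 42 − g ≥ 33, that is, while g ≤ 9.

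**Shortfall in days**

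| g | V = 25 | V = 28 | V = 30 | V = 31 |
|---|---|---|---|---|
| 0 | 0 | 0 | 0 | 0 |
| 9 | 0 | 0 | 0 | 0 |
| 10 | 1 | 1 | 1 | 1 |
| 12 | 3 | 3 | 3 | 2 |
| 14 | 5 | 5 | 3 | 2 |
| 17 or more | 8 | 5 | 3 | 2 |

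**Two readings of when participation ends**
- At the end-of-study visit: the maximum is 33 − 28 = 5 days at the nominal visit, reached from g = 14. Across the window it runs from 33 − 31 = 2 to 33 − 25 = 8 days.
- At day 30, or at the visit if later: the maximum is 33 − 30 = 3 days, reached from g = 12. With a day-31 visit it is 2.

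These figures put the last blinded dose on the day of the last treatment visit. If it was one day earlier, the visit falls on day 29 (26 to 32), and the maximum on the first reading is 4 days (1 to 7).

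**Where the uncovered days lie.** Even at V = 25 the first is day 26, after the 3-day washout. All of them lie in the 30-day ovulatory-cycle margin.

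**Can the order occur?** Section 6.1 says that for neutropenia "MMF dosing should be interrupted or the dose reduced". It sets no limit on the length of an interruption, and if dosing is never resumed the earlier dose is the final one. Its rule to discontinue study treatment for MMF intolerance is confined to Part A. Section 7.1 does not list stopping MMF as a reason to stop blinded treatment.

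**The case against.** **The order is off-plan.** MMF is scheduled for all subjects through Part B, and Section 4.1.2.1 requires that the subject is "likely to continue to tolerate the target dose through Week 52". MMF is itself investigational product (Table 5; Section 6.8), so the Section 7.1 rule to stop that product for an adverse event or laboratory abnormality could be read as ending both drugs together. This stands as a reason to call the order uncommon. It does not remove it: Section 7.1 turns on whether continued participation is in the subject's interest, and an MMF interruption under Section 6.1 does not by itself meet that test.

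**The text may already cover both drugs.** The lead-in to 4d names blinded study treatment, and a site that counted 6 weeks from whichever drug ended later would have no gap. This stands in part, and it makes the point partly one of ambiguous wording. But the lead-in defers to the items below it, and the item for women gives a length from MMF alone.

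**Five or eight days overstates it.** A reader might take these as the settled gap. The documents do not support that. Criterion 4d speaks of study participation without naming its last day, and safety follow-up runs to day 30, which caps the shortfall at 3 days. Section 4.3 also ties study completion to the last expected data collection, though it concerns the study as a whole. Both readings are open, so both sizes belong in the conclusion.

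**Redaction.** Extension-period text is removed and may contain further rules. This stands.

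**Conclusion.** The point holds as a minor drafting gap. The premise that the MMF requirement is the longer one is true on the planned course and for any MMF stop 0 to 9 days before BMS-986165. It fails from 10 days on. The shortfall is then at most 5 days if participation ends at the nominal visit (2 to 8 across the window), or at most 3 days if it runs to day 30.

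These sizes assume that MMF is not resumed, that contraception stops when participation ends, and that the last blinded dose falls on the last treatment-visit day. The number of women who would stop MMF first is not given.

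A reader might infer that women on the planned course are released too early, or that they are unprotected while drug remains in the body. Neither follows. With a same-day stop, cover runs to day 42, 9 days past day 33, and every uncovered day in the off-plan order comes after the protocol's own washout period.

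**What to change.** In criterion 4d(i) and in the Appendix 4 guidance for women, require contraception until the later of 6 weeks after the final MMF dose and 33 days after the final BMS-986165 dose. Delete the statement that the MMF requirement alone suffices for duration. The permitted methods stay unchanged.

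Cover then lasts at least to day max(42 − g, 33): day 42 at g = 0 and day 33 at every g of 9 or more, so the shortfall is zero for every stopping order and on either reading of participation.

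The cost is one sentence in each place at the next amendment, plus matching consent wording if needed (the consent pages are not visible). No visits or tests are added, and nothing changes for women on the planned course.
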